9.3 Possible Adverse Events

The following possible adverse events have been identified as possible risks from the CorMatrix ECM:

- Acute or chronic inflammation (Initial application of the CorMatrix ECM may be associated with transient, mild, localized inflammation.)
- Allergic reaction
- Bleeding
- Embolization of ECM
- Infection (superficial or deep)
- Patch dehiscence
- Pseudoaneurysm
- Recurrent stenosis
- Stroke
- Thrombosis
- Vessel occlusion

The following possible adverse events have been identified as possible risks from the surgical procedure:

- Reactions to anesthesia
- Bleeding
- Infection
- Nerve damage (skin numbness)
- Blood clots
- Hematoma
- Leg swelling
- Re-stenosis

This study will capture events reported at treatment, post-operatively, 4-6 Weeks, 6 months and 12 months follow up and as reported by the PI and/or subject and from a review of medical records.

10. Data Analysis

Since this is a Phase IV, post-market study, analyses will consist of tabulated data and descriptive statistics. Subject data listings and tabular and graphical presentations of the summary and statistical results will be provided. At a minimum, an interim report will be completed after 50 subjects have completed their four to six week follow-up. A final report will be completed at the end of the study. Additional quantitative and qualitative comparisons will be made to contemporary literature and similar studies.

11. Ethical Considerations

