The endpoint is defined as the proportion of subjects with device related adverse events.

6. Study Design

This is a multi-center, Phase IV, prospective, single arm, post-market observational study of subjects undergoing femoral arterial reconstruction using the CorMatrix ECM for vascular repair per its FDA cleared Indications for Use. It is anticipated that up to 5 eligible sites will participate enrolling up to 100 subjects. Eligible candidates will be approached to ascertain interest in study participation. The approved Informed Consent and/or Patient Information Sheet will be completed and the process will be documented in the subject study binder by the research staff. Patients who have undergone a femoral arterial reconstruction using the CorMatrix ECM will be followed as per their usual standard of care. Information will be collected at follow up visits 4-6 weeks, 6 months and 12 months.

7. Study Population

Subjects are considered to be enrolled into this study at the completion of their surgical procedure of femoral arterial reconstruction with the use of CorMatrix ECM. Before any subject can be enrolled, the IRB for the specific institution must approve the protocol and the Informed Consent/Patient Information Sheet.

Subjects must meet the following requirements to be eligible for enrollment in this study:

Inclusion Criteria:

- Subjects must be undergoing femoral arterial reconstruction with patch angioplasty closure.
- Subject's surgeon intends to use CorMatrix ECM as the patch material for femoral arterial reconstruction per its FDA cleared Indications for Use.
- The subject must possess the ability to provide informed consent.
- The subject must express an understanding and willingness to fulfill all of the expected requirements of this protocol.

Exclusion Criteria:

• Known sensitivities to porcine material

8. Study Procedures

Study procedures are standardized to the extent possible and explained in detail below and are summarized in Table I - Study Procedure Overview.

All study-related data will be captured on standardized Case Report Forms. A copy of the Case Report Forms is provided in Appendix B. Case report forms will be sent to CorMatrix via fax at [contact] (attention [name]) or via scan/email to [contact]

Activity	Pre-Tx	Treatment	Week 4-6	Month 6	Month 12
Assess Eligibility	Х				
Informed Consent Process	Х				
Medical History/update	Х	X	Х	Х	Х
Medication history/update	Х	X	Х	Х	Х
Duplex Imaging	X*		Х	Х	Х

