9.2 Assessing and Recording Adverse Events

Each AE recorded must be documented on the Case Report Form. All serious and device related events must be reported immediately to CorMatrix via telephone or email within 24 hours of the Investigator becoming aware of the event. The case report form will be submitted to CorMatrix. The site will be contacted by CorMatrix for additional information including, but not limited to:

- Description of the event and underlying cause (diagnosis), coexisting disease, or other. In order to avoid vague, ambiguous, or colloquial expressions, the AE should be recorded in standard medical terminology rather than the subject's own words when possible.
- Date of onset and date of resolution. If the event is present at the Month 12 follow-up visit it will be marked as not resolved at study exit.
- Intensity of the event: mild, moderate, or severe.
- Frequency of the event: single episode, intermittent, or continuous.
- Action taken: none, medication, procedure, medication and procedure, or other.
- Relationship to the study treatment: not-related, possibly-related, or probably-related.

Any subject withdrawn from the study due to an AE will be followed until the outcome of the event is determined. The Investigator must ensure that the details of the event are documented in the medical notes including full details of the outcome, in addition to recording the event on the appropriate case report form.

All femoral procedure and device related serious adverse events that are associated with the use of the device will be evaluated in accordance with the protocol and the Sponsor's Incident/Event Reporting SOP. Any serious adverse event that requires a Medical Device Report will be reported by the Sponsor to the FDA in accordance with Sponsor's Medical Device Reporting SOP. The site should contact:

> [name] Project Administrator, CorMatrix [contact] (direct) [contact] (company) [contact]

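### No rule requires device-event status to be established to Month 12 for subjects who leave or miss that visit, and the endpoint does not say how they are counted

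*Combined protocol and SAP*

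**What the plan says.** The endpoint (Section 5, repeated in the Synopsis) is one sentence: "The endpoint is defined as the proportion of subjects with device related adverse events". It gives no time point, no denominator and no treatment of subjects with incomplete follow-up. Section 10 adds only that "analyses will consist of tabulated data and descriptive statistics", followed by comparisons with the literature and similar studies.

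Enrollment is fixed at the end of surgery: "Subjects are considered to be enrolled into this study at the completion of their surgical procedure" (Section 7). Section 6 sets the size, "It is anticipated that up to 5 eligible sites will participate enrolling up to 100 subjects", and the schedule, "Information will be collected at follow up visits 4-6 weeks, 6 months and 12 months". Duplex imaging after surgery is scheduled only at those three visits (Table 1).

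Two passages govern event collection. Section 9.3 says "This study will capture events reported at treatment, post-operatively, 4-6 Weeks, 6 months and 12 months follow up" and continues "and as reported by the PI and/or subject and from a review of medical records". Section 9.2 has the only rule for what happens after a subject leaves: "Any subject withdrawn from the study due to an AE will be followed until the outcome of the event is determined". The protocol text available has no rule for voluntary withdrawal, missed visits, transfer of care or loss to follow-up.

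**The concern.** Everyone who receives the patch is enrolled before follow-up begins, so anyone who stops attending is already in the study. The plan does not tell the site to find out whether that person had a device event by Month 12, and does not tell the analyst what to do if the answer is unknown. A revision at another hospital need not appear in the site's records. A silent pseudoaneurysm or recurrent stenosis, both listed as device risks in Section 9.3, may be seen only on a duplex that the subject did not attend.

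This is a single-arm safety endpoint. No control group shares the under-ascertainment, and the result is to be set beside published rates. If missed events are in effect counted as non-events, the error favors the device. Events that were never collected cannot be recovered at analysis.

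**Working it through.** **1. The plan's own figures.** The protocol gives no assumed event rate, dropout rate or sample-size calculation, so there is no design figure to reproduce. The one checkable rate is in Section 4.1, for the sponsor's carotid registry: 2/186 = 1.08% with pseudoaneurysm, which agrees with the text. The denominator is all 186 enrolled patients, while that registry was still running toward 24 months. The text does not say how many had completed follow-up. The rate is then called favorable against literature rates of 1.4% to 5%. This is the only indication of how the sponsor handles incomplete follow-up, and it points to a crude proportion over everyone enrolled.

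**2. Bias if leavers are counted as event-free.** Let p be the true 12-month risk, d the fraction lost and f the fraction of lost subjects' events that are still found. With the same risk in leavers and stayers:

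expected crude proportion = p × [1 − d × (1 − f)]

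All three inputs are assumptions, except that p = 1.08% borrows the carotid figure for illustration.

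| p | d | none found (f = 0) | half found (f = 0.5) |
|---|---|---|---|
| 10% | 10% | 9.0% | 9.5% |
| 10% | 20% | 8.0% | 9.0% |
| 10% | 30% | 7.0% | 8.5% |
| 5% | 10% | 4.5% | 4.75% |
| 5% | 20% | 4.0% | 4.5% |
| 5% | 30% | 3.5% | 4.25% |
| 1.08% | 20% | 0.86% | 0.97% |

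Example: 10% × (1 − 0.20) = 8.0%; 10% × (1 − 0.20 × 0.5) = 9.0%.

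**3. If leaving is related to outcome.** Assume an overall risk of 10%, of which 2 points have occurred by the 4-6 week visit, and 25% of subjects not seen after it. With equal risk, the crude proportion is 0.75 × 10% + 0.25 × 2% = 8.0%. If leavers have twice the later risk x of stayers, then 0.75x + 0.25 × 2x = 8%, so x = 6.4%. The crude proportion becomes 2% + 0.75 × 6.4% = 6.8%. Censoring leavers at their last visit gives 2% + 6.4% = 8.4%, still short of 10%. Only finding the missing events closes the rest.

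**4. What the unstated rule alone can do.** Take 5 observed events among 100 enrolled, with 20 lost and no events recorded among them:

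- lost counted as event-free: 5/100 = 5.0% (exact 95% CI 1.6% to 11.3%)
- lost excluded: 5/80 = 6.25% (2.1% to 14.0%)
- lost all counted as events: 25/100 = 25%

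The same data support any of the three, and the plan does not choose.

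**The case against.** A reader might infer three stronger things, and the documents support none of them.

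- *That subjects who leave for reasons other than an adverse event are recorded as event-free.* The protocol does not say so. The denominator is undefined, so they could equally be excluded or handled by follow-up time. The carotid registry makes the event-free convention a likely default, not a stated rule.
- *That only adverse event withdrawals get any follow-up after exit.* Section 9.3 also names investigator report, subject report and medical records, with no attendance condition. Section 9.2 requires serious and device related events to be reported within 24 hours of the investigator learning of them. These routes may recover some events, but the text does not say that they continue after exit or when the records are read. The adverse event rule itself follows only the known event, which is already recorded, and does not extend collection of new events to Month 12. The gap therefore applies to all exits, and the contrast by reason is weak.
- *That every such exit lowers the rate.* It does not. Leaving after a recorded device event changes nothing, nor does leaving without a later event. If leavers are excluded, the proportion can rise, as step 4 shows.

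On size, a shift of 1 or 2 points is small beside the sampling error: 10/100 has an exact 95% interval of about 4.9% to 17.6%. That is fair, but the interval does not include the bias, and the bias runs in one direction under the event-free convention.

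On proportion, this is a descriptive post-market study that Section 1 says will not support a marketing claim or labeling change. That argues for a light remedy, not for leaving the endpoint undefined. The case report forms (Appendix B) are a separate document and were not available. They may contain an exit form, but that would not settle the denominator.

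**Conclusion.** The concern holds in limited form. The protocol does not require device-event status to Month 12 for subjects who leave early or miss that visit, does not say whether record review continues for them, and does not say how they enter the endpoint. If they are counted as event-free, the rate is biased low to the extent that their later events are missed. With 20% lost and between none and half of their events found, a true 10% shows as 8.0% to 9.0%, and a true 5% as 4.0% to 4.5%. The shift is larger if patients with poor results are more likely to leave, and close to nil if loss is small or record review is thorough. The risk, the loss and the fraction found are assumptions. The direction depends on the event-free convention, which the protocol suggests only indirectly.

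**What to change.** **Sections 8.4 and 9.2: one exit rule for all reasons.** For every enrolled subject without a Month 12 visit, the site completes the Month 12 adverse event form from medical records and one telephone contact, within the limits of the subject's continuing consent. It records the reason for exit, the date last known event-free, vital status and any groin re-operation.

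**Section 10: define the estimate.** State that the denominator is all enrolled subjects. Report the 12-month cumulative incidence of a first device related adverse event, censored at the date last known event-free, with death as a competing event. Show the crude proportion and the number of exits by reason beside it. Onset dates are already collected under Section 9.2. If every subject is followed to Month 12 or death, the two estimates coincide.

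**State the limits.** Censoring assumes that leaving is uninformative, which step 3 shows can matter. A call or record review does not replace the Month 12 duplex for silent events.

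**Cost.** One record review and one call per non-attender, using a source that Section 9.3 already names; one extra table; and possibly a slightly higher reported rate.

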4.1 Post-market Clinical Evaluation of the ECM for Carotid Repair

CorMatrix is currently conducting a post-market registry study for the CorMatrix ECM for Carotid Repair (Protocol No. 11-PR-1021). The objective of this registry is to capture and assess device performance data from subjects undergoing patch angioplasty of the carotid artery following carotid endarterectomy using the CorMatrix ECM for Carotid Repair per its commercial Indications for Use. This registry provides an ongoing post-market surveillance mechanism to document clinical outcomes on the use of the CorMatrix ECM for Carotid Repair. This is a multi-center, prospective, single-arm, post-market, observational registry of subjects receiving the CorMatrix ECM for Carotid Repair for patch angioplasty following carotid endarterectomy procedures. This post-market registry may involve up to ten U.S. clinical sites and up to 230 subjects. Data will be collected through the 24-month follow-up.

One-hundred and eighty six patients are enrolled in the study and included in the interim analysis of the CorMatrix ECM for Carotid Repair registry. The data demonstrated that the rate of device related adverse events were consistent with the rates found in the review of the contemporary literature for patch angioplasty. Specifically, no unanticipated events were found and the rate of the events was as anticipated in the risk management plan. Of specific interest in the analysis was the rate of pseudoaneurysm, which was present in 2 (1.08%) of the 186 patients and compared favorably to the rates found in the literature (1.4% to 5%).

The mean carotid stenosis (maximum) at pre-operative was 85.5%. Mean change from baseline values were -52.5%, -53.9%, -58.4%, and -45.2% at the 1- to 3-month, 6-month, 12-month, and 24-month follow-up evaluations. The mean carotid stenosis (minimum) at pre-operative was 72.5%. Mean change from baseline values were -64.5%, -63.7%, -

63.2%, and -60.4% at the 1- to 3-month, 6-month, 12-month, and 24-month follow-up evaluations.

As a result of this analysis and the directed and ongoing risk management activities, the overall residual risk of the CorMatrix ECM for Carotid Repair is determined to be acceptable.

5. Study Objectives

The objective of the study is to actively gather additional information on the use of CorMatrix ECM for vascular repair in the reconstruction of the femoral artery.

Endpoint

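### Section 10 promises quantitative comparisons of a single-arm study with outside sources, but requires no confidence interval and sets no comparator selection rule in advance

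*Combined protocol and SAP*

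**What the plan says.** Section 10 (Data Analysis) is one paragraph and refers to no separate analysis plan. It states that "analyses will consist of tabulated data and descriptive statistics", provides for listings, tables and graphs, and sets two reports. For the first: "At a minimum, an interim report will be completed after 50 subjects have completed their four to six week follow-up". The second is a final report at study end. The paragraph closes with the commitment at issue: "Additional quantitative and qualitative comparisons will be made to contemporary literature and similar studies".

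No confidence interval, confidence level or other measure of precision is required. No source, reference rate, selection rule or time point for the comparison is given.

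Section 5 sets the quantity to be reported: "The endpoint is defined as the proportion of subjects with device related adverse events". Section 6 describes a single-arm design and gives a ceiling on size: "It is anticipated that up to 5 eligible sites will participate enrolling up to 100 subjects". Follow-up runs to 12 months.

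Two literature ranges appear as background: femoral primary patency of 74% to 91% at 5 years (Section 1) and carotid pseudoaneurysm of 1.4% to 5% (Section 4.1). Section 10 designates neither as a comparator, and neither matches the endpoint in outcome and follow-up.

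**The concern.** With one arm, any comparison has to be external. Two things then decide how the result reads: how precisely this study estimates its own rate, and which published rate is set beside it. Section 10 leaves both open.

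A bare percentage from 50 or 100 subjects can sit below a published figure when the data are equally compatible with rates above it. If sources are chosen once the results are known, the choice can settle the impression.

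What is at stake is the wording of the interim and final reports. No hypothesis, performance goal, margin or stopping rule depends on either report.

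**Working it through.** **Inputs**
- Endpoint: one proportion of subjects (Section 5).
- Interim size: 50 subjects who have completed the 4-6 week visit (Section 10). This is the trigger for the report. Using 50 as the denominator is an assumption.
- Final size: 100, which is a ceiling (Section 6).
- Carotid registry: 2 pseudoaneurysms in 186 patients, literature range 1.4% to 5% (Section 4.1).
- Confidence level: two-sided 95%. The documents give none, so this is an assumption.
- Femoral adverse event rate: none given in the documents.

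**Step 1: reproduce the stated rate.** 2/186 = 0.01075, or 1.08% after rounding, as in Section 4.1.

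**Step 2: method.** The exact (Clopper-Pearson) limits for x events in n subjects solve
- lower limit L: P(X ≥ x | n, L) = 0.025
- upper limit U: P(X ≤ x | n, U) = 0.025

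For x = 0 the lower limit is 0 and U = 1 − 0.025^(1/n).

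**Step 3: the carotid illustration.** For x = 2, n = 186 the limits are 0.13% and 3.83%. A Wilson interval gives 0.30% to 3.84%, so the reading does not depend on the method. Section 4.1 says that pseudoaneurysm was "present in 2 (1.08%) of the 186 patients and compared favorably to the rates found in the literature (1.4% to 5" per cent). The interval lies below 5% but contains 1.4% and much of the range. The summary shows no interval, so as written the favourable reading rests on the point estimate.

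**Step 4: the planned sizes.**
- 0/50: U = 1 − 0.025^(1/50) = 7.11%
- 1/50: 0.05% to 10.65%
- 0/100: U = 1 − 0.025^(1/100) = 3.62%
- 1/100: 0.03% to 5.45%

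**Step 5: scale.** The carotid range is borrowed for scale only, since it concerns one event type in another artery. Against it, zero events in 50 would not exclude 5%. Zero in 100 would exclude 5% but not 1.4%. One event in 100 gives an interval containing the whole range. The same data could therefore look favourable or not, depending on which published rate is placed beside them.

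**The case against.** The strongest reply is that nothing inferential is planned. The stated objective is to gather further information, Section 1 says the data will not support a marketing claim or labeling change, and placing a descriptive rate beside published ones is itself descriptive. Section 10 does not forbid an interval, and a reader given counts can compute one. All of this is correct, and it keeps the point modest. It does not remove it: an interval is also descriptive, and a reader cannot reconstruct afterwards how the sources were chosen.

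Several stronger readings are tempting and are not supported.

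- *A reader might infer a power or regulatory error.* The plan has no hypothesis, margin or decision rule for such an error to affect.
- *A reader might infer that these sample sizes make a falsely favourable result unusually likely.* When the true rate equals the comparator, the observed rate falls below it about half the time at any size. With a true rate of 1.4% this happens in 45% of samples of 500 and 48% of samples of 5000. Such figures do not measure a weakness of this study.
- *A reader might infer that the interim denominator is a defect of its own.* The endpoint is a proportion of subjects, and Section 7 supplies a natural default: "Subjects are considered to be enrolled into this study at the completion of their surgical procedure". Printing the denominator is enough.
- *A reader might infer that the carotid conclusion was wrong, or that it predicts the femoral reports.* Section 4.1 summarises another protocol and artery, the full registry report is not in the documents, and its interval does exclude 5%. It shows only how such a comparison can be worded.

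**Conclusion.** The point holds as a modest weakness in precision and comparator selection that is cheap to correct. Section 10 commits the study to quantitative external comparison and requires neither an interval nor a selection rule fixed beforehand.

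Its size is the width of the intervals: even with no events, the upper bound is 7.1% at 50 subjects and 3.6% at 100. Fewer subjects than the ceiling would widen the final interval.

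This rests on the assumed 95% level, on 50 and 100 as denominators, and on treating published rates as fixed numbers, which ignores their own sampling error. No figure here is anchored to a femoral adverse event rate, because the documents contain none.

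**What to change.** Add to Section 10:

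- (a) In both the interim and final reports, give the endpoint, and any device event compared with an outside rate, as count, denominator and two-sided 95% confidence interval (for example exact). Show the interval beside every comparison.
- (b) Write down the rule for selecting comparator sources, with event definition and matching follow-up time, before accumulated outcome data are reviewed. Tying this only to the interim report date would be too late: the sponsor is its own data coordination center, receives the case report forms, and is told of serious and device related events within 24 hours (Section 9.2). Later literature may be added under the same rule and labelled as such, which keeps the final comparison contemporary.
- (c) Do not describe a result as favourable when its interval contains the comparator rate. In the carotid example, this would allow saying that 2/186 is below 5%, but not that it is favourable to the whole 1.4% to 5% range.

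The cost is a few sentences, trivial computation and an earlier decision about sources. No patients or visits are added. The downside is a little more reporting work and less favourable comparative wording.

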9.1 Definitions

Adverse Event (AE)

An adverse event (AE) will be defined as any undesirable clinical occurrence in a subject whether it is considered to be device related or not, that includes a clinical sign, symptom, or condition/observation of an unintended technical performance or performance outcome of the device. Causality is defined as not-related, possibly-related and probably-related to the device, which is further defined in Table 2: Event Relationship Assessment.

Serious Adverse Event (SAE)

A serious adverse event ("SAE") will be defined as an event that: 1) threatens life, 2) results in permanent impairment of a body function or permanent damage to a body structure, 3) necessitates medical or surgical intervention to preclude such impairment, 4) requires or prolongs hospitalization, or 5) is fatal (death).

Adverse Device Event

An Adverse Device Event will be defined as a clinical sign, symptom, or condition that is causally related to the device procedure, the presence of the device, or the performance of the device. Due to the temporal proximity of the AE to product administration, there is a reasonable possibility that the product may have caused the AE or may have contributed to the severity or duration of an event caused by other means.

AE Relationship	Description			
Not-related	A temporal relationship to the use of the product, which makes a			
	causal relationship clearly and incontrovertibly due to extraneous			
	causes, such as other drugs, products, chemicals, underlying			
	diseases, environment, etc. Not-related to the use of the product.			
Possibly-related	Occurring within a reasonable period of time relative to the use of			
	the product, which makes a causal relationship possible, but			
	plausible explanations may also be provided by other causes,			
	such as other drugs, products, chemicals, underlying disease,			
	environment, etc. Possibly-related to the use of the product.			
Probably-related	Occurring within a reasonable period of time relative to use of			
	product, which makes a causal relationship probable where the			
	relationship cannot be attributed to other causes, such as drugs,			
	products, chemicals, underlying disease, environment, etc.			
	Probably-related to the use of the product.			

Table 2: Event Relationship

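### The planned literature comparison has no rule that both sides use the same attribution rule; setting a device related rate against rates counted regardless of attribution would flatter the patch

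*Combined protocol and SAP*

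**What the plan says.** - **Endpoint** (Synopsis; Section 5): "The endpoint is defined as the proportion of subjects with device related adverse events". No other endpoint is named.
- **Analysis** (Section 10): "analyses will consist of tabulated data and descriptive statistics", followed by "Additional quantitative and qualitative comparisons will be made to contemporary literature and similar studies". The measure, event types, time point and sources for these comparisons are not given.
- **Size and follow-up** (Section 6): a single arm "enrolling up to 100 subjects", with visits at 4-6 weeks, 6 months and 12 months.
- **Relatedness** (Section 9.1, Table 2; Section 9.2): three grades, namely not-related, possibly-related and probably-related, obtained from the site. No independent adjudication is described. The documents do not say whether possibly-related counts as device related for the endpoint.
- **Capture**: Section 9.1 defines an adverse event "whether it is considered to be device related or not". Section 9.2 sends each recorded adverse event to the case report form, and Section 8.3 collects any complications or adverse events up to discharge. The Synopsis and Section 8.2 mention only device related events.
- **Precedent** (Section 4.1, carotid registry): "the rate of device related adverse events were consistent with the rates found in the review of the contemporary literature for patch angioplasty". The same section reports pseudoaneurysm in 2 of 186 patients (1.08%) against a literature range of 1.4% to 5%.

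**The concern.** A device related rate has passed through a filter: an event counts only if it is attributed to the device. A published series of another patch cannot have rated relatedness to this device under this protocol's Table 2. If that series counts infections, bleeds, pseudoaneurysms and occlusions as they occur, the two numerators measure different things, and the filter can only remove events from the study side.

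This is separate from the absence of a confidence interval or a named comparator. With both supplied, the numerators would still differ, and an interval around the filtered rate would make a misleadingly favourable result look more secure. At stake is the safety reading of the study. In the carotid registry, comparisons of this kind fed a conclusion that residual risk was acceptable.

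**Working it through.** **1. The plan's own figure.** 2/186 = 1.075%, which reproduces the 1.08% in Section 4.1. Its exact (Clopper-Pearson) 95% interval is 0.13% to 3.83%, so it includes the lower literature value of 1.4%. The plan states no sample-size, power or alpha calculation to reproduce.

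**2. Inputs for the filter effect.**
- n = 100: the maximum enrolment in Section 6.
- p, the true rate of an event type, equal here and in the literature: not in the documents. Assumed 8%, with 5% and 10% to show sensitivity.
- s, the share of affected subjects whose event is rated device related: not in the documents. Shown from 1 down to 0.25.
- Literature rates counted regardless of attribution: assumed.

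**3. Formula.** The number of subjects counted is X ~ Binomial(100, s × p). The expected observed rate divided by the literature rate is s × p / p = s. Two chances follow:
- A: the observed rate is at most half the literature rate. At p = 8% this is P(X ≤ 4).
- B: the whole exact 95% interval lies below the literature rate. With 2 events in 100 the upper limit is 7.0%; with 3 it is 8.5%. At p = 8% this is therefore P(X ≤ 2).

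**4. Results at p = 8%, equally performing patch.**

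| s | Expected observed rate | A | B |
|---|---|---|---|
| 1 | 8.0% | 9% | 1% |
| 0.9 | 7.2% | 15% | 2% |
| 0.75 | 6.0% | 28% | 6% |
| 0.5 | 4.0% | 63% | 23% |
| 0.25 | 2.0% | 95% | 68% |

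**5. Sensitivity to p.** For s = 1, 0.9, 0.75, 0.5 and 0.25 in turn:
- p = 10%: B, here P(X ≤ 4), is 2%, 5%, 12%, 44% and 89%.
- p = 5%: B, here P(X = 0), is 1%, 1%, 2%, 8% and 28%.

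**6. How strong the filter could be under Table 2.** Not-related requires a cause that is clearly and incontrovertibly extraneous. If possibly-related counts as device related, few events at the patch would be removed and s may be close to 1. Probably-related requires that the event cannot be attributed to other causes. If only that grade counts, the filter is severe: Section 9.3 lists bleeding and infection as risks of both the device and the surgery, and stenosis likewise, so an alternative explanation is usually at hand. The choice between these two readings largely determines s, and the documents do not make it.

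**The case against.** A reader might infer that the plan compares a filtered rate with unfiltered literature by construction, and that the filtered rate is the only one the study will have. The documents do not support that.

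- Section 10 does not name the rate compared. The device related proportion is the only named endpoint, not the only possible rate. Table 1 schedules duplex imaging, infection information and adverse event assessment, and Section 10 promises tabulations and listings, so rates by event type regardless of attribution are compatible with the plan.
- The precedent is mixed. The general sentence in Section 4.1 concerns device related events, but its one numerical safety comparison, pseudoaneurysm, is worded as occurrence.
- Nothing states that the literature rates are unfiltered. The similar studies could include the carotid registry, which also reports device related events.
- The high bar for not-related, together with an Adverse Device Event definition that reaches the device procedure, may leave s near 1. At s = 0.9 and 8%, chance B is 2% against 1% unfiltered, which is negligible.
- Scheduled duplex may find events that sources without scheduled scanning would miss. That pushes the other way, so the net direction of all differences is not fixed.
- The comparison is additional to a descriptive analysis, and Section 1 rules out use for marketing claims or labeling.

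All of this stands, and it limits the point to a conditional one. It does not remove it: the plan permits the mismatch, the sponsor has reported a comparison in that form, and Section 1 says the study will evaluate safety and effectiveness.

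**Conclusion.** The concern holds in conditional form. Section 10 commits to quantitative comparison with literature and does not require the same attribution rule on both sides. Whenever a device related rate is set against rates counted regardless of attribution, an equally performing patch looks better by the factor s.

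The size depends on assumed values. With 100 subjects and 8% on both sides, the chance of seeing half the literature rate or less rises from 9% with no filter to 28% at s = 0.75 and 63% at s = 0.5. There is no bias at s = 1 and little at 0.9. The direction of the attribution effect is fixed only if the literature counts events as they occur, which is an assumption. Which relatedness grades count is the open question that most affects the size. Given the descriptive purpose of the study, this is a change the sponsor should make, not a defect that invalidates the design.

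**What to change.** 1. Add to Section 10: *Comparisons with literature and similar studies use the proportion of subjects with each event type (for example pseudoaneurysm, infection, bleeding, thrombosis or occlusion, recurrent stenosis) regardless of the relatedness rating. The device related proportion is reported as the endpoint and is compared only with sources that applied a comparable attribution rule.*
2. State whether possibly-related events count as device related.
3. Reconcile the Synopsis and Section 8.2, which mention only device related events, with Sections 8.3, 9.1 and 9.2, so that all adverse events are captured on the case report form. This has to be settled first: without full capture, the like-for-like rates may not be recoverable later.

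The cost is two sentences in Section 10, one clarification of the endpoint and a consistency edit on capture. The downside is that the compared rates will be higher, and so less favourable, than the device related proportion. Scheduled duplex may also raise them above sources without scheduled scanning, which the report should note. A form field recording whether an event was found by scheduled scan or by symptoms would help separate these, but it is optional: the case report forms are a separate document not available here, and they may already have one.
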